v. EEG-based connectivity analysis offers superior temporal specificity for the study of IEDs. Assessment of IEDs using fMRI is limited by the poor temporal specificity of fMRI. IEDs last hundreds of milliseconds whereas blood flow changes measured by fMRI require multiple seconds. In contrast, EEG is a temporally-precise method for studying the impact of IEDs on network connectivity.[37] High-density EEG (HD-EEG) specifically estimates the underlying source of this activity. Surprisingly, however, few EEG connectivity analyses have been done in children with BECTS.[38–41] Only one study assess the impact of IEDs in wakefulness and it is limited by a small sample size of children with only right hemispheric IEDs, thus obscuring the impact of IEDs on language network connectivity. Furthermore, all EEG connectivity studies in BECTS have been done in the resting state, whereas language network connectivity is likely to be better measured when the network is engaged in a task. Therefore, a significant gap persists in understanding connectivity in BECTS.

EEG connectivity analysis has been limited by the concern for volume conduction, a problem that arises when activity in nearby electrodes is correlated not because the regions are connected but rather because the electrodes are picking up neuronal activity from a single common source. Fortunately, new connectivity metrics, such as the **weighted Phase Lag Index (wPLI)**,[42] are quite robust against volume conduction. To calculate wPLI, the EEG signal is broken down into frequency bands (i.e. alpha, beta) and the phase of the waveforms in each band is compared across brain regions; non-zero phase lags are considered true connectivity.[42] wPLI is a continuous metric ranging from 0-1, where 0 indicates no connectivity and 1 indicates perfect connectivity. wPLI offers better spatial-specificity when it is calculated from a high number of EEG electrodes.

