vi. Combining transcranial magnetic stimulation with EEG (TMS-EEG) will shed new insight into BECTS by directly probing the epileptogenic motor cortex. TMS is the only non-invasive method to directly interrogate the influence of one brain region over another. Single pulses of TMS (spTMS) introduce a current into the stimulated cortex, the immediate downstream effect of which can be mapped by EEG on the order of milliseconds.[20] The strength of the magnetic pulse required to induce a muscle twitch (typically in an intrinsic hand muscle like the abductor pollicis brevis [APB]) is known as the **motor threshold (MT)**. The EEG data recorded immediately after TMS pulses can also be analyzed with connectivity measures like wPLI. Additionally, TMS elicits **motor evoked potentials (MEPs)** recorded by surface EMG as well as **TMS-EEG evoked potentials (TEPs)** broadly across the brain. Finally, **repetitive trains of TMS (rTMS)** induce long-lasting changes in brain excitability,[43,44] and inhibitory rTMS can reduce IED frequency in epilepsy patients.[21,45] rTMS can therefore be used to model how changes in IED frequency affect brain connectivity.

Significance

The impact of IEDs on children with BECTS and other epilepsies is not understood. We typically do not treat IEDs due to our poor understanding of their significance. In this trial, we will evaluate if rTMS could be a treatment for focal IEDs in pediatric epilepsy and will assess the impact of such a treatment on the language network. Successful completion of the proposed studies will determine if IEDs directly alter connectivity between the motor and language regions in children with BECTS, if such connectivity differences persist even during IED-free periods, and whether connectivity differences correlate with language dysfunction. We will utilize rTMS as a novel method to suppress IEDs in BECTS in order to determine if rTMS could be a treatment for focal IEDs and what the impact of such treatment on the language network might be. Together, these data lay the groundwork for highly innovative future neurostimulation trials targeting IEDs in not only BECTS but also a wide range of pediatric epilepsy syndromes.

RISKS/BENEFITS

Potential Risks:

- (1) Risks of EEG Recording: EEG does not cause harmful effects, though some children may find the EEG caps uncomfortable.

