To evaluate if rTMS reduces connectivity between the motor and language regions in children with BECTS.	Change in weighted phase lag index (wPLI) (an EEG-based connectivity measure) between the stimulated motor cortex and the left inferior frontal gyrus induced by active rTMS vs. sham rTMS. Change will be calculated by comparing wPLI in the 20 minutes after rTMS vs. the 20 minutes before rTMS. We will collect 2 types of EEG data before and after the active/sham rTMS: (a) spTMS-EEG, and (b) resting-state EEG; and Connectivity will be calculated for each of these data types separately.	This endpoint will help us determine the downstream effect of rTMS on other brain networks.	Epilepsy is a network disorder and fMRI studies suggest that IEDs from the motor cortex increase connectivity between the motor cortex and inferior frontal gyrus. Therefore, inhibition of IEDs and increased inhibition of the motor cortex may decrease connectivity between the motor cortex and inferior frontal gyrus.

STUDY DESIGN

Overview: Children with BECTS will undergo both active rTMS and sham rTMS to the epileptogenic motor cortex. We will compare the impact of active vs. sham rTMS on: (a) IED frequency; and (b) motor-to-language connectivity. We hypothesize that active rTMS induce a greater decrease in: (a) IED frequency and (b) motor-to-language cortex connectivity than sham rTMS.

Study Stage: Stage 0

Study Design: Sham-controlled cross-over study in which all participants will receive both active and sham rTMS, with randomization of order of intervention. We will have repeated-measures data as subjects will undergo both sham and real rTMS on different days. The potential missing data issue will be evaluated thoroughly prior to the analysis. Multiple imputation will be applied if needed.

Assignment Methods: Not applicable, subjects will undergo both active and sham rTMS.

Study Arms: All subjects will participate in each arm, and arm order will be randomized on a per-subject basis. Participation in each arm will take approximately 4 hours (including set-up of equipment and data recording). Arms will be separated by at least 1 week.

Arm 1 (active rTMS): 1000 pulses of rTMS administered via an active TMS coil at 1Hz to the motor cortex. EEG and spTMS-EEG data will be recorded during the 20 minutes prior to and following the rTMS.

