Active rTMS: The active intervention is 1Hz rTMS applied with an active coil to the motor cortex. Low frequency (1Hz or slower) rTMS can induce changes in brain excitability lasting minutes to hours [43,44] and has been shown to reduce IED frequency in patients with refractory focal epilepsy.[21,45] Focal changes induced by rTMS have downstream effects on brain regions connected to the stimulated motor cortex. Theoretically, 1Hz active rTMS will reduce cortical excitability of the epileptogenic motor cortex, thus reducing IED frequency. Furthermore, it will alter connectivity between the epileptogenic motor cortex and other connected cortices. Thus, we are measuring IED frequency and EEG-based connectivity.

Sham rTMS: The sham control is 1Hz rTMS administered with a sham coil, which will help account for the impact of other components of the experimental session (i.e. fear, boredom, variable attention).

rTMS Administration: The rTMS (sham and active) will be administered by a study team including [name] and a research assistant over the course of 2 sessions separated from one another by at least a week. This will occur in a room dedicated to the TMS session. The rTMS will be administered as 2 blocks of 500 pulses applied at 1Hz to the motor cortex. A break of 2-3 minutes between blocks is acceptable if needed to allow for maximum participation. The sham rTMS will be administered using the same parameters and same stimulation site, but the intensity of the sham coil is such that it is not expected to induce an intracranial current.

RANDOMIZATION & BLINDING:

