First rTMS Session: BECTS subjects will wear a 64-channel TMS-compatible high-density EEG cap while watching a video and listening to white noise. We will use neuro-navigation software to co-register the head and electrode positions to a representative pediatric brain or to the subject's MRI if one is clinically available. At the beginning of the session, we will monitor the EEG recording to determine if IEDs are unilateral or bilateral. We will then measure the resting motor threshold (rMT) for the hemisphere with the higher IED burden or the left hemisphere if IEDs are bilateral. The rMT will be established in the standard way.⁵⁵ We will apply 150 single pulses of TMS (spTMS) at 90% rMT in 2 blocks, with additional resting-state EEG (without spTMS) data gathered between these blocks. The patient will then receive either 1000 pulses of 1Hz rTMS at 90% rMT or 1000 pulses of sham 1Hz rTMS to the motor cortex, depending on the prior randomization. After the rTMS, we will repeat the blocks of spTMS interspersed with resting-state EEG.

Second rTMS Session: The second session will occur at least one week after the first session, but ideally will be done within 2-4 weeks of the first. In the second session, the procedures will be repeated as above except the other intervention will be administered. Of note, occasionally IED-predominance shifts hemispheres between EEGs. We will stimulate the same side as received rTMS during the first session unless >80% of IEDs are emerging from the contralateral hemisphere. If this occurs, we will stimulate the contralateral hemisphere and request that the subject come in for a third “tie-breaker” session.

REFERENCES

- [3] Wirrell EC. Benign epilepsy of childhood with centrotemporal spikes. *Epilepsia* 1998;39 Suppl 4:S32-41.

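### On single-pulse TMS-EEG, wPLI can shift because the pulse-evoked response shifts, with no change in motor-to-language coupling, and the sham contrast does not remove this

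*Protocol*

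**What the plan says.** The second row of the Protocol's Objectives & Endpoints table defines the endpoint as "Change in weighted phase lag index (wPLI) (an EEG-based connectivity measure) between the stimulated motor cortex and the left inferior frontal gyrus", active against sham. It adds: "We will collect 2 types of EEG data before and after the active/sham rTMS: (a) spTMS-EEG, and (b) resting-state EEG". wPLI is to be calculated on each type separately.

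Literature Review item v defends wPLI against volume conduction and gives its interpretation: "non-zero phase lags are considered true connectivity". Item vi extends the measure to post-pulse recordings: "The EEG data recorded immediately after TMS pulses can also be analyzed with connectivity measures like wPLI". The same item states that pulses produce evoked potentials over wide areas of the brain.

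Study Procedures (First rTMS Session) sets the probe: "We will apply 150 single pulses of TMS (spTMS) at 90% rMT in 2 blocks". Justification for Study Design and Dose gives the expected action: "Theoretically, 1Hz active rTMS will reduce cortical excitability of the epileptogenic motor cortex, thus reducing IED frequency". Under Randomization & Blinding, the sham coil is meant to be felt on the scalp but to drive no current in the brain.

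Neither document gives a post-pulse window, says whether the mean evoked response is removed before wPLI is computed, plans a comparison of evoked amplitude before and after rTMS, or says how the spTMS and resting-state results will be read against each other. The SAP tests 15 region pairs without saying which EEG type they come from.

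**The concern.** The defence offered for wPLI concerns signals that reach several electrodes from one source with no delay. A TMS pulse is a different kind of common cause. It triggers both regions at the same instant, and each may respond with its own latency. The resulting phase lag is non-zero and repeats on every pulse, so it meets the protocol's criterion for connectivity whether or not one region acts on the other.

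The sham arm would cancel this if the evoked response changed equally in both sessions. The protocol's rationale implies otherwise: active rTMS should lower motor cortex excitability and sham should not. If lower excitability means a smaller evoked response (an inference, though a natural one), wPLI can differ between conditions for that reason alone, often in the hypothesised direction. The trial could then report a change in the motor-to-language network when it has shown a change in the response to the probe pulse.

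**Working it through.** The documents contain no wPLI value, evoked amplitude, SD or power calculation, so there is no planned figure to reproduce. The check is a simulation.

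**Inputs from the documents.** 150 pulses. The wording also allows 75 or 300 per analysis; both were run. 36-40 children, crossover. Wilcoxon signed-rank test on active change minus sham change.

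**Assumptions.** wPLI is taken across pulses, and the mean response is not removed. Evoked amplitude *a* is in units of background SD (complex band signal with mean squared magnitude 1) and the evoked lag φ is fixed. Alpha is 0.05 two-sided for one pair.

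**Model.** Per pulse, X = a₁ + noise and Y = a₂·exp(-iφ) + noise; wPLI = |mean Im(XY*)| / mean |Im(XY*)|. With independent noise the expected numerator is a₁·a₂·sin φ. It contains no coupling term, yet it is non-zero unless φ is 0 or 180 degrees.

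**Step 1: zero coupling, 150 pulses, a₁ = a₂ = a.**

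| a | φ = 0° | φ = 45° | φ = 90° |
|---|---|---|---|
| 0 | 0.09 | 0.09 | 0.09 |
| 0.25 | 0.09 | 0.11 | 0.13-0.14 |
| 0.5 | 0.09 | 0.28 | 0.39 |
| 1 | 0.09 | 0.67 | 0.84 |
| 2 | 0.09 | 0.96 | 1.00 |

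Pulse number mainly moves the floor: about 0.13 at 75 pulses and 0.065 at 300.

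**Step 2: smaller evoked response, still zero coupling.** A 25% fall in both regions at 45° takes wPLI from 0.28 to 0.18 (a = 0.5), 0.67 to 0.50 (a = 1), 0.96 to 0.88 (a = 2) and 1.00 to 0.98 (a = 3). A 30% fall in the motor cortex alone at a = 1 takes it from 0.67 to 0.56 (45°) and from 0.84 to 0.73 (90°).

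**Step 3: constant true coupling.** Let the backgrounds correlate at c = 0.3 with a 60° lag. wPLI is 0.49 with no evoked response. With evoked lag 45° in the same direction, a 25% fall moves it from 0.64 to 0.58 (a = 0.5) and from 0.84 to 0.75 (a = 1). If the lags oppose, the numerator is a²·sin 45° - 0.3·sin 60° = 0.707a² - 0.260, which is zero near a = 0.61. Below that point a smaller response raises wPLI: 0.15 at a = 0.5, 0.40 at a = 0.25.

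**Step 4: the planned test.** Zero coupling, N = 36, between-child log-SD of *a* 0.5, evoked amplitude falling after active only. Chance that active and sham differ at 0.05:

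| Scenario | median a = 0.5 | a = 1 | a = 2 |
|---|---|---|---|
| No fall | 0.05 | 0.05-0.07 | 0.05 |
| 10% fall, both regions, 45° | 0.21 | 0.58 | 0.70 |
| 25% fall, both regions, 45° | 0.79 | 1.00 | 1.00 |
| 25% fall, motor cortex only, random lag per child | 0.25-0.32 | about 0.7 | 0.83 |

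Ranges span repeat runs. In the last row every significant result was a decrease.

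**Step 5: subtracting each region's mean evoked response.** With identical responses on every pulse, wPLI returns to 0.09 at zero coupling for every *a*, and to 0.49 at c = 0.3 whatever the evoked amplitude. Pulse-to-pulse variation that is independent in the two regions (30%) also leaves 0.09. Variation shared by both regions does not cancel: the residual numerator is CV²·a₁·a₂·sin φ. At CV 0.5 and a = 1, subtracted wPLI is about 0.28 (45°) and 0.38 (90°), and a 30% motor-only fall still lowers it to about 0.21 and 0.29. At CV 0.3 the residual is 0.13-0.17.

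**The case against.** The strongest reply is that the evoked response is what TMS-EEG is there to measure. The protocol uses single pulses to see how one region acts on another. If the frontal response is the motor cortex pulse arriving there, a weaker response is partly a real change in effective connectivity, and subtracting it discards signal. This stands in part, and it is why the unsubtracted value should be kept. But wPLI alone cannot separate weaker propagation from a smaller local response: in the motor-only runs the frontal response was held constant and wPLI still fell.

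Other points also stand. Probe pulses are below motor threshold, so evoked amplitude may be small; at 0.25 background SD the effect barely clears the floor. White noise and noise-cancelling headphones reduce the auditory part of any shared response. Resting-state EEG already supplies a pulse-free comparison.

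A reader might infer that post-pulse wPLI mainly reflects time-locking, or that a smaller response must lower it. The documents support neither. They give no evoked amplitude; at a = 0.5 with c = 0.3, true coupling still supplies most of the value; the effect vanishes at zero lag, is slight near saturation and can reverse. A reader might also infer that the plan leaves the evoked response in. The documents do not say either way.

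**Conclusion.** The concern holds in a limited form. As described, spTMS wPLI can move because the evoked response moves, and comparison with sham does not protect against this, because the protocol itself expects only active rTMS to lower excitability. This is more than a missing detail: it affects what a positive spTMS result would mean.

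The size cannot be fixed from the documents. It runs from negligible (a = 0.25) to large (a = 1 or more), given wPLI taken across pulses, no removal of the mean response, and a lag other than 0 or 180 degrees. The size of any fall in evoked amplitude after active rTMS is likewise assumed. The resting-state half of the endpoint is untouched, so it would be wrong to conclude that the connectivity endpoint as a whole is compromised.

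**What to change.** For the spTMS-EEG data:

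- State the post-pulse window, and which EEG type the SAP's 15 pairs come from.
- Report wPLI both with and without subtraction of each region's trial-mean evoked response, computed per child, session and pre/post period.
- Report evoked amplitude at the motor cortex and the inferior frontal gyrus before and after each condition.
- Describe a change seen only in unsubtracted wPLI as a change in the pulse-evoked response, covering local excitability or propagation.
- Claim altered motor-to-language coupling only where the subtracted spTMS wPLI and the resting-state wPLI support it.

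The cost is a modest re-analysis of EEG the protocol already collects, and possibly a less favourable result. Since shared pulse-to-pulse variation can survive subtraction, the subtracted value should be read beside the resting-state result and not made the sole decisive measure.

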Arm 2 (sham rTMS): 1000 pulses of rTMS administered via a sham TMS coil at 1Hz to the motor cortex. EEG and spTMS-EEG data will be recorded during the 20 minutes prior to and following the rTMS.

Control Groups: As above, each subject will receive sham rTMS and thus serve as their own control. This within-subject analysis is meant to reduce the influence of inter-subject variability in IED frequency (which can be high) on the results. A potential limitation is that a sham-control may be excessively stringent, given that other studies have found clinically meaningful improvements when sham rTMS is used (i.e. in post-stroke motor recovery), suggesting that even sham rTMS can exert a meaningful physiologic influence. A second limitation is that IED frequency and connectivity may be influenced by behavioral state, which may change between days or behavioral states; we will interact with participants and monitor EEG to maintain behavioral state.

rTMS Intervention: The 1000 pulses of 1Hz rTMS will be delivered in 2 blocks of 500 pulses administered over a total of 16-20 minutes. Changes in cortical excitability after 1Hz rTMS typically last approximately the duration of the rTMS itself, so we will measure changes to IEDs and connectivity in the 15-20 minutes directly before and after rTMS. If a subject only tolerates 500 pulses, we will restrict measurements to the 10 minutes before and after the rTMS; we will shorten the second intervention accordingly. If a subject does not tolerate 500 pulses, they will be excluded for inability to tolerate the protocol. We will separate the active and sham rTMS session by at least 1 week to ensure adequate wash-out of effects, as is standard in rTMS trials.

RECRUITMENT & RETENTION

Anticipated number to be screened: We expect to recruit 36-40 subjects and anticipate screening 70-80 subjects to reach this target enrollment.

Anticipated Sample Size: We expect to recruit 36-40 subjects over 4 years, at a rate of 9-10 subjects per year. Subjects will be between the ages of 5-16 years. Based on the typical epidemiology and presenting age of BECTS, we expect 60-70% of subjects to be male and 80% of subjects to be between the ages of 7-12 years. Based on the demographics of the patient

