The order of conditions (active vs. sham rTMS) will be randomized on a per-subject basis. A random number generator will be used to create a random list using numbers 1-40. Subjects whose recruitment lines up with an even number will receive active rTMS in the first session and sham rTMS in the second session and vice versa for odd numbers. Participants will be blind to the condition order. The sham rTMS will be administered using the same parameters and same stimulation site as the active stimulation. The intensity of the sham coil is such that it is expected to create a scalp sensation without inducing an intracranial current. It is possible that some subjects will recognize a difference between the 2 sessions, and we will ask them after each session to assess if it was active vs. sham rTMS. If subjects can consistently identify a difference, than we will report that blinding was not successful in our final analyses.

Researchers will not be blinded during the session, but the data will be coded prior to analysis and the person performing the analysis will be blinded to the session type.

STUDY PROCEDURES

Screening: For subjects referred by their physician, the study team will confirm the diagnosis of BECTS with the referring provider. Parents of participants will then be called by a member of the research team and screened on the inclusion and exclusion criteria. If the parents primarily speak a different language than English, the screening will be conducted with the help of an interpreter or by a study team member fluent in that language.

For subjects who self-refer to the study, the study team will review the inclusion and exclusion criteria with the family. Subjects who screen-in and consent to the study will be asked to bring a physician's note stating their diagnosis and prior EEG findings.

Screening will be done within 2 months of participation. If this time window is delayed, the inclusion/exclusion criteria will be reviewed on the day of the first intervention to ensure the subject is still eligible.

Informed Consent & Assent: Since informed consent is required from both parents and/or legal guardians if they are reasonably available (i.e. not deceased, imprisoned, whereabouts unknown or not involved in the care of the child), informed consent will be first obtained over the telephone with the help of an interpreter if necessary. Assent will be obtained from the participating child on the day of the first rTMS session.

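### Must behavioural state be scored by session and window before the active-versus-sham comparison can be relied on?

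*Protocol*

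**What the plan says.** The Protocol raises the issue itself. Under Study Design, Control Groups, it gives as a limitation that "IED frequency and connectivity may be influenced by behavioral state, which may change between days or behavioral states", and answers that "we will interact with participants and monitor EEG to maintain behavioral state". The Overview describes the discharges as sleep-potentiated.

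Other parts of the plan bear on the same risk:

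- **Timing.** Under rTMS Intervention, "we will measure changes to IEDs and connectivity in the 15-20 minutes directly before and after rTMS". If a child tolerates only the first block of pulses, "we will restrict measurements to the 10 minutes before and after the rTMS", and the second session is shortened to match.
- **Standardisation.** Under First and Second rTMS Session, the child watches a video and hears white noise, and the second visit repeats the procedures with the other coil. Protection Against Risk adds that staff talk with the child and that an epileptologist is present with the EEG actively monitored.
- **Sham.** Under Sham rTMS, the sham coil is there to absorb non-specific session effects, including boredom and fluctuating attention.
- **Blinding.** "Participants will be blind to the condition order". "Researchers will not be blinded during the session", but the data are coded and "the person performing the analysis will be blinded to the session type".
- **Analysis.** The SAP uses Wilcoxon signed-rank tests, first post against pre within each session, then active change against sham change. It does not mention state.

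**The concern.** A factor that the sponsor says can move both outcomes would normally be measured. Here it is only managed, by people who know the condition. If they kept children more alert in one condition than in the other, or if the two coils felt different enough to change alertness, spike counts and connectivity could differ after rTMS for reasons unrelated to cortical inhibition. Coding the data before analysis would neither remove nor reveal this, because the difference would already be in the recording.

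The SAP's sham post-versus-pre test would pick up some drift. It could not say whether drowsiness or the sham itself was responsible, since the Protocol cites sham improvements in other studies, "suggesting that even sham rTMS can exert a meaningful physiologic influence". At stake is whether a positive or null contrast could be partly a difference in alertness, with no planned figure to check it.

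**Working it through.** The documents give no figure to reproduce: no alpha, effect size, standard deviation or state multiplier. The check therefore asks which state differences survive the design, how large they could be, and what scoring would add.

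**1. What cancels.** Write the mean outcome in session c and window w as a base level, plus a day effect for c, plus a drift for w common to both sessions, plus the rTMS effect (active post window only), plus a remaining state term s(c,w). Then

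(active post − active pre) − (sham post − sham pre) = rTMS effect + g,

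where g = [s(active, post) − s(active, pre)] − [s(sham, post) − s(sham, pre)].

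The day effect and the additive common drift both drop out. Only g remains: a change in state between windows that differs by condition.

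**2. Simulation.** Signed-rank test, two-sided 0.05 (assumed), no true effect, 20,000 runs, n = 38 (the middle of the planned 36-40). Offsets are in SDs of the paired difference of changes.

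| State offset | Rejection rate |
|---|---|
| 0.5 SD in both windows of the active day | 5.1% |
| 0.3 SD in the active post window only | 42.7% |
| 0.5 SD in the active post window only | 83.4% |

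A whole-day difference does no harm. A condition-linked change between windows would, if it existed.

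**3. Size on the spike scale.** Assume discharges are k = 2, 3 or 5 times as frequent when drowsy, and that 10% of each pre window is drowsy. A window with drowsy fraction p has rate r[1 + p(k − 1)], with r the awake rate.

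- *Systematic gap of 10 points after rTMS:* shift = 0.10(k − 1)/[1 + 0.10(k − 1)] = 0.1/1.1, 0.2/1.2, 0.4/1.4 = 9%, 17%, 29% of the pre rate. It is zero if there is no gap or k = 1.
- *Random gap, mean zero, SD 10 points:* no bias. The standard-error component runs from 0.091/√40 = 1.4% to 0.286/√36 = 4.8% of the pre rate. This is ordinary noise, already in the data that the test uses.
- *Common drift from 10% to 30% drowsy:* sham post against pre rises by 1.3/1.1 − 1, 1.6/1.2 − 1, 2.2/1.4 − 1 = 18%, 33%, 57%. With no true effect the contrast stays at zero. With a true 25% fall that acts multiplicatively, it reads −0.25 × 1.182, 1.333, 1.571 = −30%, −33%, −39%: right sign, inflated size.

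No magnitude is available for an effect of state on wPLI.

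**4. What scoring would add, and its price.**

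- *Reading time:* 36 × 4 × 15 min = 36 h at the least and 40 × 4 × 20 min = 53 h at the most, less for any child on shortened windows.
- *Awake-only wPLI:* with no coupling, wPLI from N independent epochs averages about 1/√N. That is 0.082 at 150 epochs, 0.086 at 135 and 0.098 at 105, the last two being 90% and 70% of 150 pulses. Dropping drowsy epochs unevenly would therefore create differences unless counts were matched.
- *Acting on a sign change:* suppose whole-window and awake-only estimates correlate 0.80 to 0.95 (assumed, bivariate normal). With no true effect, their signs differ with probability arccos(ρ)/π = 0.6435/3.1416 to 0.3176/3.1416, about 20% to 10%. A disagreement would often be chance.

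**The case for a change.** The strongest case for acting is that the sponsor named the factor, the people controlling it are unblinded, and the Protocol (Randomization & Blinding) concedes that some children may tell the sessions apart. The recordings exist, so blind marking needs no new visit. Balanced percentages of awake time would strengthen the result, and imbalance would let the conclusion be qualified honestly.

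Part of this stands. Unequal handling by unblinded staff is a real route to bias that neither randomised order nor analyst blinding closes, and a short descriptive table of percent awake, labelled post hoc, would do no harm.

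The rest does not carry through. Nothing in the documents indicates unequal handling. If active stimulation itself changes alertness, the resulting change in discharges belongs to its total effect, so restricting to awake epochs would condition on something the intervention may have altered. Such an analysis could be supportive at most. The SAP is a two-paragraph summary in the past tense and does not describe EEG preprocessing or epoch selection, so its silence does not show that state was ignored when the recordings were read. Common drift does distort the within-session tests, but the objective in the endpoints table is the active-versus-sham contrast, which the SAP tests directly.

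**Conclusion.** No change to the plan is needed. The observation is accurate: state is acknowledged and managed live, but no scoring or report by session and window is written down. It does not follow that the comparison is unsound. Sham control, own-control change scores, random order, blinded children, repeated procedures and a blinded analyst remove or balance the state differences that a crossover of this kind would ordinarily meet. What remains is a condition-linked change in alertness between windows. The documents do not show one, and the 9% to 29% shift rests wholly on an assumed multiplier, an assumed baseline and an assumed 10-point gap.

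This is a fair trade-off. The limitation is disclosed and managed. Formal scoring would cost roughly 36 to 53 reader hours in a Stage 0 study whose SAP already reads as completed work, would leave the whole-window endpoints as they are, and would yield only descriptive results. The study team may choose to tabulate percent awake, but the validity of the planned contrast does not depend on it. The judgement assumes that staff handled active and sham sessions alike, as the repeated procedures imply. Evidence to the contrary would reopen the question.
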